8.2.1 Physical Examinations

- A complete physical examination will include, at a minimum, assessments of the cardiovascular, respiratory, gastrointestinal and neurological systems.
- A brief physical examination will include, at a minimum, assessments of the skin, lungs, cardiovascular system, and abdomen (liver and spleen).
- Investigators will pay special attention to clinical signs related to previous serious illnesses.

8.2.2 Vital Signs

- Blood pressure and participant's position during measurement; pulse; respiratory rate; temperature and location of measurement, weight, and height (at Baseline only) will be measured and recorded.

Vital signs will be measured in supine position.

- Blood pressure and pulse measurements will be preceded by at least 5 minutes of rest for the participant in a quiet setting without distractions (e.g. television, cell phones) and measured with an automated device. Manual techniques will be used only if an automated device is not available.

8.2.3 Electrocardiograms

Single 12-lead ECG will be obtained as outlined in the SoA and will be preceded by at least 5 minutes of rest for the participant in a quiet setting without distractions (e.g. television, cell phones).

Together with the ECG recorders also laptops, a server laptop and printer will be provided by the ECG core lab. With the aid of this setup, site personnel will be able to trigger and print 12-lead safety ECGs directly from the Holter devices using the laptops. A detailed manual for this process will be supplied by the ECG core lab. An on-site training will be done prior to study start.

Detailed information on Holter ECGs is given in Section [8.4.3](#).

8.2.4 Clinical Safety Laboratory Tests

- Blood and urine samples will be collected for the clinical laboratory tests listed in [Appendix 6](#) at the timepoints listed in the SoA. All samples will be clearly identified.
- Additional tests may be performed at any time during the study, as determined necessary by the Investigator or required by local regulations.
- The tests will be performed by Nuvisan GmbH laboratory; the QuantiFERON® Test will be performed by Synlab, Augsburg, Germany.
- The Investigator will review each laboratory report, document this review, and record any clinically significant changes occurring during the study as an AE, unless it does **not** meet the AE definition, as specified in [Appendix 4](#). The laboratory reports will be filed with the source documents.

- Laboratory results that could unblind the study will not be reported to investigative sites or other blinded personnel until the study has been unblinded (see Section 6.3.2 and 6.3.3).

8.3 Adverse Events, Serious Adverse Events, and Other Safety Reporting

- The definitions of an AE and SAE are in [Appendix 4](#).
- The Investigator and any qualified designees (e.g. Subinvestigators) are responsible for detecting, documenting, and recording events that meet the definition of an AE or SAE. The Investigator remains responsible for following up AEs that are serious, considered related to the study intervention or study procedures, or that caused the participant to discontinue the study intervention or study, as specified in Section 8.3.2.
- Requests for follow-up will usually be made via the Sponsor or CRO-designated study team member, although in exceptional circumstances the global patient safety department may contact the Investigator directly to obtain further information or to discuss the event.
- The method of recording, evaluating, and assessing causality of AEs and SAEs and the procedures for completing and transmitting SAE reports are in [Appendix 4](#).
- All AEs and SAEs will be collected from the signing of the ICF until the safety follow-up call at the timepoints specified in the SoA (Section 1.3). Beyond this reporting period, any new unsolicited SAEs that the Investigator spontaneously reports to the Sponsor will be collected and processed.
- All SAEs will be recorded and reported to the Sponsor or designee immediately and under no circumstance will this exceed 24 hours, as indicated in [Appendix 4](#). The Investigator will submit any updated SAE data to the Sponsor within 24 hours of it being available using the same procedure that was used for the initial report.
- Investigators are not obligated to actively solicit information on AEs or SAEs after the end of study participation. However, if the Investigator learns of any SAE, including a death, at any time after a participant has been discharged from the study, and he/she considers the event to be reasonably related to the study intervention or study participation, the Investigator will promptly notify the Sponsor.

8.3.1 Method of Detecting Adverse Events and Serious Adverse Events

At each study visit, the participant will be queried on changes in his or her condition.

Care will be taken not to introduce bias when detecting AEs and/or SAEs. Open-ended and non-leading verbal questioning of the participant is the preferred method to inquire about AE occurrences.

The method of recording, evaluating, and assessing causality of AEs and SAEs and the procedures for completing and transmitting SAE reports are in [Appendix 4](#).

8.3.2 Follow-up of Adverse Events and Serious Adverse Events

After the initial AE/SAE report, the Investigator is required to proactively follow each participant at subsequent visits/contacts. All SAEs, and AESIs (as defined in Section 8.3.7), will be followed until resolution, stabilization, the event is otherwise explained, or the participant is lost to follow-up (as defined in Section 7.3). Reasonable attempts to obtain this information will be made and documented. It is also the Investigator's responsibility to ensure that any necessary additional therapeutic measures and follow-up procedures are performed. Further information on follow-up procedures is in [Appendix 4](#).

8.3.3 Regulatory Reporting Requirements for Serious Adverse Events

- Prompt notification by the Investigator to the Sponsor of an SAE (particularly life-threatening and deaths) is essential so that legal obligations and ethical responsibilities toward the safety of participants and the safety of a study intervention under clinical investigation are met.
- The Sponsor has a legal responsibility to notify both the local regulatory authority and other regulatory agencies about the safety of a study intervention under clinical investigation. The Sponsor will comply with country-specific regulatory requirements relating to safety reporting to the regulatory authority, IRB/IEC, and Investigators.
- Individual Case Safety Reports will be prepared for SUSARs according to local regulatory requirements and Sponsor policy and forwarded to Investigators within 15 days.
- An Investigator or Subinvestigator who receives an Individual Case Safety Report describing a SUSAR or other specific safety information (e.g. Emerging Safety Issue Report, summary or listing of SAEs/SUSARs) from the Sponsor will read it and confirm completion of this activity. This information will be filed in the Investigator's Site File, and the IRB/IEC will be notified, if appropriate, according to applicable local laws/regulations and site SOPs.

8.3.4 Pregnancy

- Details of all pregnancies in female participants will be collected after the start of study intervention and until the Safety Follow-up. Note: In this study, only women of nonchildbearing potential will be included.
- If a pregnancy is reported, the Investigator will record the pregnancy information on the appropriate form and submit it to the Sponsor within 24 hours of female participant pregnancy.
- While pregnancy itself is not considered to be an AE or SAE, any pregnancy complication or elective termination of a pregnancy will be reported as an AE or SAE. Adverse pregnancy outcomes (e.g. spontaneous abortion, fetal death, stillbirth, congenital anomalies, ectopic pregnancy) are considered and reported as SAEs. A spontaneous abortion (occurring at < 22 weeks gestational age) or stillbirth (occurring at > 22 weeks gestational age) is always considered to be an SAE and will be reported as such.
- The participant will be followed to determine the outcome of the pregnancy. The Investigator will collect follow-up information on the participant and the neonate, and the information will be forwarded to the Sponsor. Generally, follow-up will not be required for longer than 6 to

8 weeks beyond the estimated delivery date for a healthy newborn. In case of a congenital anomaly or other illness of the newborn, follow-up will continue until the illness has resolved or there is a definite outcome of the event.

- Any post study pregnancy related SAE considered reasonably related to the study intervention by the Investigator will be reported to the Sponsor as specified in Section 8.3.3. While the Investigator is not obligated to actively seek this information in former study participants he or she may learn of an SAE through spontaneous reporting.
- Any female participant who becomes pregnant while participating in the study will discontinue study intervention or be withdrawn from the study.

8.3.5 Cardiovascular and Death Events

Not applicable.

8.3.6 Disease-Related Events and/or Disease-Related Outcomes Not Qualifying as AEs or SAEs

Not applicable.

Asymptomatic elevations in amylase or lipase or both in participants treated with evobrutinib have been observed at a variety of time points and reported as TEAEs or noted as laboratory abnormalities. In RMS Study MS200527_0086, the incidence of TEAEs of lipase increased was slightly higher in evobrutinib 75 mg once daily and 75 mg twice daily arms (5 [9.4%] and 5 [9.3%], respectively) when compared to other arms (approximately between 4% to 6%). However, shifts from Baseline to highest grade on treatment were similar across all treatment arms for both amylase and lipase. In evobrutinib studies in other indications and in healthy participants, the incidence of TEAEs of increased amylase or lipase, or both was infrequent and no clinically meaningful differences were observed across treatment arms. Any elevation of $> 2 \times$ ULN of lipase or amylase and any type of pancreatitis are classified as AESIs.

- Liver related events

The elevations of transaminases observed in participants treated with evobrutinib were frequent, asymptomatic, and reversible on discontinuation of evobrutinib. The mechanism is unknown.

Evobrutinib liver AESIs will include transaminases ($> 3 \times$ ULN), bilirubin elevations ($> 1.5 \times$ ULN), biological Hy's Law cases based on laboratory data, any type of acute or chronic hepatitis (any grade), suspected drug-induced liver injury, acute or chronic hepatic failure, fibrosis, cirrhosis, and other liver damage-related conditions.

AESIs have to be reported immediately (within 24 hours). For reporting of AESIs, see [Appendix 4](#).

8.4 Pharmacokinetics

8.4.1 Blood Sampling and Bioanalysis

- Samples are collected only where allowed by local law/regulations.

- The actual date and time (24-hour clock time) of:

- Each sample collection
 - Study intervention administration prior to sample collection

will be recorded in the eCRF to determine the elapsed time of sampling in relation to the administration of study intervention.

- Blood samples for measurements of plasma evobrutinib CCI [REDACTED] and moxifloxacin concentrations will be collected. Collection times are specified in the SoA.

- The actual date and time (24-hour clock time) of:

- start and end of each blood collection interval

- study intervention administration prior to sample collection
 - the volume of each blood collection fraction

will be recorded in the eCRF, in order to determine the elapsed time of sampling in relation to the administration of study drug. The accepted time deviations from planned PK sampling times that will not be considered a protocol violation are listed in [Table 1](#).

- The quantification of evobrutinib and moxifloxacin in plasma will be performed using a validated assay method. **CCI**

[REDACTED]. Retention time and possible analyses of samples after the end of study are specified in the respective ICF.

- Details on processes for collection and handling of these samples are in the Laboratory Manual.

Table 1 Time Deviations from PK sampling times

Procedure	Time Point (Relative Time)	Window Allowance
PK	Predose	- 15 min
	15 min	± 2 min
	30 min	± 2 min
	1 hr	± 2 min
	1.5 hr	± 5 min
	2 hr	± 5 min
	2.5 hr	± 5 min
	3 hr	± 5 min
	4 hr	± 5 min
	6 hr	± 5 min
	8 hr	± 5 min
	12 hr	± 5 min
	16 hr	± 15 min
	24 hr	± 15 min

8.4.2 PK Parameters

- The following PK parameters for evobrutinib, its major metabolite, and moxifloxacin will be calculated, when appropriate:

Symbol	Definition
AUC ₀₋₂₄	The partial AUC from time zero (= dosing time) to 24 hours.
AUC _{0-t_{last}}	The AUC from time zero (= dosing time) to the time of the last quantifiable concentration (t _{last}).
AUC _{0-∞}	The AUC from time zero (= dosing time) up to infinity with extrapolation of the terminal phase.
AUCextra%	The AUC from time t _{last} extrapolated to infinity given as percentage of AUC _{0-∞} .
C _{max}	Maximum observed concentration.
CL/F	The apparent total body clearance following extravascular administration (parent only).
λ _z	Terminal first order (elimination) rate constant.
T _{max}	The time to reach the C _{max} in a dosing interval.
T _{1/2}	The terminal half-life.
V _z /F	The apparent volume of distribution during the terminal phase following extravascular administration (parent only).

Other PK parameters might be added based on emerging data. Details will be in the IAP.

- Concentration data may be used for integrated data analyses across studies, such as population PK and exposure-response analyses of PD biomarker, QTc, efficacy and/or safety analyses and reported separately from the main CSR.

8.4.3 Electrocardiograms

In this study, ECGs will be recorded using standard 12-lead ECG devices and 12-lead Holter recorders for the following purposes:

- Check of eligibility of a participant for the study during screening using standard 12-lead ECG machines (single ECGs).
- Immediate safety assessment at the site using safety single 12-lead ECGs that are being printed from the Holter recordings.
- Extraction of triplicate 10 s ECGs from continuous Holter recordings for central evaluation and statistical analyses of possible drug effects on cardiac safety parameters.

The standard ten seconds 12-lead ECGs will be recorded by devices (CardioPerfect, Hillroom, Chicago, USA) supplied by the site at times indicated in the Flow Chart. These ECGs will be acquired using Goldberger/Einthoven and Wilson leads in supine position (small pillow under head allowed) and after a rest for at least 15 min. The devices will print the ECGs for immediate evaluation by the investigator or his/her designee. The following automatically calculated parameters will be used: Ventricular rate, PR interval, QRS duration, QT interval (uncorrected) and QTcB and QTcF.

The evaluation by the Investigator includes an overall assessment (normal, description of abnormality including clinical relevance) which will be entered into the eCRF system.

The 12-lead Holter ECGs will be recorded using devices (CM3000 or Seer 12, getemed AG, Berlin, Germany), supplied by the ECG core lab (nabios GmbH, Munich, Germany). All devices will be tested prior to shipment and installed at the site. An on-site training will be performed for the site staff. Details of the ECG recordings and data transfer procedure will be supplied in manuals.

For these continuous recordings modified Goldberger/Einthoven (so-called Mason-Likar) lead positions and Wilson chest leads will be used. The recordings will be started approximately 2 h before the corresponding time point of the planned time of administration on Day -1 and will end shortly after the 24 h time point postdose. At least 15 min prior to the extraction time points the participants have to be in supine position in a quiet environment. This resting period is followed by another 3 min term during which the participant should be at complete rest with no interventions. At the end of this period, the study staff will press the marker button on the recorder to flag this electronically on the ECG signal. Immediately afterwards, further planned measurements and blood samplings will be performed. After the recordings are done, the data will be transferred to the core lab using one of the laptops and a pre-installed and tested data transfer program. At the core lab, triplicate 10 s ECGs with approximately 1-minute time difference between 2 successive ECGs will be extracted from the 12-lead Holter recordings guided by the electronic markers. The timing of the markers will be tested by the core lab staff by checking the markers with the respective nominal times of the individual medication times. In case inconsistencies are detected, the core lab will query the site.

After the ECG have been extracted at the core lab, they will be measured for cardiac intervals RR, PR(Q), QRS, and QT from 4 preferably consecutive heart beats in lead II. If lead II is not evaluable in an ECG lead V or lead I will be used. All ECGs of a particular participant will be measured in the same lead. The measurement will be done using the core labs validated semi-automated programs and procedures. The end of the T wave will be determined using the so-called slope (or tangent) method. This method approximates the downslope of the T wave by a linear function. The end of the T wave is then defined as the crossing point between this straight and the isoelectric line. All fiducial point markings will be reviewed by trained technicians.

Within the ECG laboratory, the staff involved with ECG interval measurements and morphological analyses will be blinded with regard to treatment, date and time as well as time points of the ECG measurements. No more than 2 blinded readers will evaluate all ECGs of the study. The interval measurements for a given participant will be performed in random and blinded sequence by a single reader. For quality assurance and control of the measurements, all ECGs of an individual participant will be subsequently reviewed by the ECG technician supervisor or his/her designee to assess the overall variance of the measured intervals and to detect accidental switching of leads and/or false participant assignments of the ECGs.

In addition to the measurements of the intervals, one randomly selected ECG at each time point will be evaluated by a board-certified cardiologist. This evaluation will include an overall assessment as well as specific findings regarding rhythm, conduction, ST-T segment and T/U-wave, morphology, and myocardial infarction. Standard CDISC terms will be used for this interpretation of the ECG. The cardiologist will review the ECGs one by one and in random order. Thus, she/he is practically blinded to the sequence of the ECG within a participant. After

evaluation of the ECGs, the results will be submitted to the data management company using a predefined data transfer method and specification. The transfer will include for any ECG recording classified as “abnormal” the description of the abnormality in addition to the clinical relevance (yes/no).

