Triplicate ECGs from Holter recordings			X	X		X	X		X	X		X	X		On each dosing day 12-lead ECGs extracted in triplicates from Holter recordings at 3 timepoints before dosing (-1 h, -30 min, and -10 min), and at 15 and 30 min and 1, 1.5, 2, 2.5 3, 4, 6, 8, 12, 16 h and at 24 h postdose.
Clinical laboratory safety tests	X	X			X			X			X		X		Blood samples for the clinical laboratory safety assessments will be collected in a fasted condition.
PK sampling (evobrutinib, evobrutinib major metabolite, and moxifloxacin)			X	X		X	X		X	X		X	X		Plasma samples for PK analysis will be collected on the days of dosing (i.e., Days 1, 8, 15, and 22) at predose and 15 and 30 min, and 1, 1.5, 2, 2.5, 3, 4, 6, 8, 12, 16 and 24 h postdose. At visits where assessment time points coincide with each other, the following sequence of activities will be followed: PK sample to be collected shortly (within time windows specified) after ECG.
Study intervention administration			X			X			X			X			
Previous/concomitant medication monitoring	X	<=====>													Section 6.8.
AE monitoring	X	<=====>													Section 8.3.

CRU=clinical research unit; ECG=electrocardiogram; eGFR=estimated glomerular filtration rate; FSH=follicle stimulating hormone; PK=pharmacokinetics; SARS-CoV-2=severe acute respiratory syndrome coronavirus 2; TSH=thyroid stimulating hormone.

2

[figure not shown]
Introduction

Evobrutinib is an oral, selective, irreversible inhibitor of BTK that is in clinical development for the treatment of autoimmune diseases, e.g. RMS. Detailed information on the chemistry, pharmacology, efficacy, and safety of evobrutinib is in the current IB.

This study is being conducted to assess potential effects of evobrutinib on cardiac repolarization (i.e., prolongation of QT interval).

CC1

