- Evobrutinib and placebo solution will be administered after reconstituting API (or placebo) in 100 mL buffer. A second bottle of buffer will be used to rinse the bottle with reconstituted API (or placebo) twice (50 mL each time). The participants will then receive 40 mL of water to reach a total volume of 240 mL. Further details are provided in the IMP handling manual.
- All treatments will be administered following an overnight fast (10 h). Subjects will not be allowed any liquid from 1 h predose until 1 h postdose, except for the 240 mL water and buffer required to consume the dose with. Subjects will remain fasting until 4 h postdose.
- To mask the taste of the active compound, both the active compound and placebo will contain orange flavor to allow identical taste. The placebo oral solution will be matched for appearance and volume in order to maintain the blind.
- Moxifloxacin dose will be administered together with a total amount of 240 mL water in a standing position.

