16.1.4 General Specifications for PK Concentration and PK Parameter Data

Predose samples that occur before the first drug administration will be assigned a time of 0 hours, as if the sample had been taken simultaneously with the study intervention administration. Same applies to the predose sample after multiple doses.

Predose or trough samples which have been taken after the subsequent dosing will be reported as a protocol deviation. The resulting concentrations will be included in concentration listings but excluded from descriptive statistics of concentrations and from PK parameter estimation.

Values BLQ will be taken as zero for summary statistics of PK concentration data, PK parameter estimation (e.g., AUC) and for graphical presentations.

Missing concentrations (e.g., no sample, insufficient sample volume for analysis, no result or result not valid) will be reported generally as "N.R.". A participant who withdraws prior to the last planned observation will be included in the analyses up to the time of discontinuation if still included in the PK analysis set.

If samples are collected outside the PK sampling time windows defined in the CSP in Section 8.4, these will be included in the PK parameter estimation (NCA) but will be excluded from the concentration summary and mean/median concentration plots.

PK concentrations which are erroneous due to a sampling processing or analytical error (as documented in the bioanalytical report) may be excluded from the PK analysis if agreed by the Sponsor. In this case the rationale for exclusion will be provided in the CSR. Any other PK concentrations that appear implausible to the Clinical Pharmacologist/Clinical PK/PD Scientist will not be excluded from the analysis. Any implausible data will be documented in the CSR.

If important protocol deviations occurred likely to affect the PK profile of participants as specified in Section 10.2.1, the impacted concentrations and PK parameters will be excluded from summary statistics and further statistical evaluation.

Any PK concentrations or PK parameters excluded from summary statistics will be included in participants listings and flagged; a reason for exclusion will be detailed in the CSR (e.g., a footnote or a table of exclusions). Any flags will be included in the study specific CDISC data sets.

PK concentrations and PK parameters excluded from summary statistics will not be included in mean/median figures. Mean plots will only contain values where $n > 2$.

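### Does the supine-rest rule spoil the 15-minute ECG after moxifloxacin, given that the tablet is taken standing?

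*Protocol*

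**What the plan says.** On rest before each extracted ECG, Protocol 8.4.3 states "At least 15 min prior to the extraction time points the participants have to be in supine position in a quiet environment" and continues "This resting period is followed by another 3 min term during which the participant should be at complete rest with no interventions". The marker is pressed at the end of that term, and then "Immediately afterwards, further planned measurements and blood samplings will be performed".

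On dosing, Protocol 6.1 states "Moxifloxacin dose will be administered together with a total amount of 240 mL water in a standing position". It gives no posture for the evobrutinib or placebo solutions.

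On timing, the Schedule of Activities (Protocol 1.3) places triplicate ECGs at three pre-dose times "and at 15 and 30 min and 1, 1.5, 2, 2.5 3, 4, 6, 8, 12, 16 h and at 24 h postdose". It orders the two measurements: "PK sample to be collected shortly (within time windows specified) after ECG". Protocol 8.4.1 says "The accepted time deviations from planned PK sampling times that will not be considered a protocol violation are listed in" Table 1, which allows ± 2 minutes at the 15-minute sample.

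On handling, SAP 16.3.1 matches ECG and PK by nominal time and flags an ECG record for exclusion only when the two are more than 15 minutes apart. For PK samples outside their window, SAP 16.1.4 says "these will be included in the PK parameter estimation (NCA) but will be excluded from the concentration summary and mean/median concentration plots". SAP 10.2.1 gives an open-ended list of deviations for case review, and individual values may be flagged. SAP 8.1 removes participants from the C-QTc analysis for deviations likely to affect comparability.

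**The concern.** A participant who stands to swallow a tablet at time 0 cannot also have been lying down for the 15 or 18 minutes before an ECG at 15 minutes. Staff must shorten the rest, or take the ECG late and risk missing the PK window. Because the schedule itself causes this, it would recur in every moxifloxacin period.

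A recent change of posture can disturb heart rate and the QT measurement. If placebo were given in a different posture, the 15-minute moxifloxacin-minus-placebo difference could carry an artefact. That would enter the 15-minute by-timepoint summary, and the intercept and slope of the moxifloxacin C-QTc model used to show assay sensitivity. No visible sentence in the SAP names this record, and a severe reading of SAP 8.1 could turn a shortfall built into the schedule into exclusion of participants.

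**Working it through.** **Timing.** Inputs: 15 minutes supine and 3 minutes complete rest (Protocol 8.4.3); standing dose at time 0 (6.1); first ECG at 15 minutes (1.3); latest on-window PK sample at 15 + 2 = 17 minutes (Table 1). Required start of rest = ECG time - rest needed.

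| ECG time | 15 + 3 = 18 min in sequence | 15 min in total |
|---|---|---|
| 15 min | 15 - 18 = -3 min (conflict) | 15 - 15 = 0 min (no time to dose) |
| 17 min | 17 - 18 = -1 min (conflict) | 17 - 15 = +2 min (feasible) |
| 30 min | 30 - 18 = +12 min | 30 - 15 = +15 min |

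All later times and the three pre-dose times are feasible, so 1 of 13 post-dose times (7.7%) is affected.

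**Size of the shortfall.** The ECG 10 minutes before dosing carries the same rest rule, so in sequence the participant is already supine from -28 to -10 minutes. Suppose the participant lies down again 1 minute after the dose (an assumption). Rest is then 15 - 1 = 14 minutes at nominal time and 17 - 1 = 16 minutes at the window edge. Against 18 minutes the deficit is 4 or 2 minutes; against 15 minutes it is 1 or 0.

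**What the SAP does with the record.**

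- Rest taken in full from time 0 puts the marker at 18 minutes, with the blood draw immediately after. The ECG-PK gap is far below 15 minutes, so SAP 16.3.1 retains the pair.
- The sample falls at least 18 - 17 = 1 minute outside its window. Under SAP 16.1.4 it leaves the concentration summary and the mean and median plots, but stays in the NCA, which uses actual elapsed times (SAP 16.1.5.1). Nothing visible removes it from the C-QTc match.
- If instead the ECG is taken on time after slightly less rest, the pair is also retained, unless data review flags it.

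**Effect on assay sensitivity.** The criterion (Protocol 9.4.2) is the lower 90% bound of the model prediction at the observed geometric mean Cmax. A least-squares check used fixed effects for nominal time, treatment and concentration, fitted to moxifloxacin and placebo at the 13 times. A 1 ms bias was placed in the 15-minute moxifloxacin value only.

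Shift at Cmax = change in intercept + Cmax × change in slope, with Cmax = 3.1 mg/L (Protocol 2.2). Assumptions: one-compartment PK, absorption rate 0.8 to 3 per hour, half-life 8 to 12 hours, lag 0 to 0.25 hours, 32 participants, and a treatment intercept (the SAP's equation is blacked out). The two extremes are:

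- Rate 0.8, half-life 8, lag 0.25: 0.302 - 3.1 × 0.119 = -0.067 (-0.065 with unrounded coefficients).
- Rate 3, half-life 8, no lag: 0.133 - 3.1 × 0.025 = +0.056 (+0.057 unrounded).

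The unrounded range is therefore -0.065 to +0.057 ms per 1 ms. For an assumed 5 ms artefact this is 5 × (-0.065) = -0.33 ms to 5 × 0.057 = +0.29 ms. Early in absorption the concentration is low, so the bias raises the intercept and flattens the slope, and the two largely cancel at Cmax.

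A wider grid, with half-life 8 to 16 hours and tmax spanning 0.50 to 3.88 hours, gives -0.51 to +0.73 ms with a treatment intercept and +0.14 to +0.63 ms without one. If placebo carries the same artefact, the time effects absorb it and the shift is 0.00 ms.

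For scale, the pooled moxifloxacin effect quoted in Protocol 4.2.1 is 12.3 ms at 3 hours, which is 12.3 - 5 = 7.3 ms above the threshold before any allowance for the confidence interval.

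**Effect on the primary analysis.** Evobrutinib and placebo are both solutions, matched for appearance and volume and given double-blind, so the documents give no reason for them to differ in posture. The treatments listed for the primary model's diagnostics (SAP 16.3.3.4) are placebo and the two evobrutinib doses, not moxifloxacin.

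**The case for a change.** The strongest case for acting is that the contradiction is not a matter of interpretation. Read in sequence, the rest rule, the standing dose and the PK window cannot all be honoured, and the same breach recurs for every participant. A line in the protocol, a sentence in the SAP and one extra model fit without the 15-minute point would cost little. In that fit the standard error at Cmax would rise by about 0 to 7%. Any moxifloxacin-placebo artefact would also pass undiluted into the 15-minute by-timepoint difference.

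The textual conflict stands, and so does the point about the by-timepoint value. But that value is descriptive, and it could matter to the tabulated maximum only if it overtook the times around the moxifloxacin peak, which Protocol 2.2 puts at 0.5 to 4 hours.

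The rest does not hold up. Record-level handling already exists in SAP 16.3.1 and 10.2.1, so a further sentence would only name a timepoint. SAP 8.1 is limited to deviations likely to affect comparability, and nothing shows that a few minutes less rest would qualify. Applied to a shortfall common to every moxifloxacin period, it would empty the analysis set, which no data review would sensibly do. The core lab also checks markers against nominal times and queries inconsistencies (Protocol 8.4.3), which would catch a late marker, though not a posture. The extra fit is optional: no one has shown an artefact for it to detect.

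**Conclusion.** No change to the plan follows. The sections are inconsistent at one of 13 post-dose times in the moxifloxacin period, by 3 minutes at nominal time if the rest periods run in sequence, and by up to 2 minutes of lateness if they overlap. This is an operational wording slip. Staff can take the ECG as close to nominal time as practicable, and the SAP's existing rules keep the ECG-concentration pair or allow a single value to be flagged.

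The assay-sensitivity prediction would move by a few tenths of a millisecond for an assumed 5 ms artefact, and by at most about 0.7 ms over the wide range. No effect on the evobrutinib conclusion is shown.

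This rests on assumed PK shapes, an assumed model form and an artefact whose size and sign are unknown. The ECG and IMP handling manuals and the blacked-out parts of SAP 16.3 may settle the detail. Should the protocol be reopened for another reason, Sections 1.3, 6.1 and 8.4.3 ought to be reconciled then; which posture or rest rule is right is not a matter for this review.
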